6.2 Screening Phase

Following written informed consent, and unless otherwise specified, the following assessments will be performed during the 28 day period prior to the first dose of rucaparib. Assessments performed within this window, but prior to patient signing informed consent, are acceptable only if confirmed to have been standard of care.

Alterations to re-consenting patients:

In cases where a face-to-face scenario is not deemed practical or safe for re-consenting subjects, the study team will send the Informed Consent Form to patients in a way that is practical and convenient (e.g., email/scan or fax). In place of the face-to-face scenario, the appropriate delegated study personnel will explain the changes to the Informed Consent Form by way of a telephone call with the patient. After the re-consent discussion, the participant will be asked to sign the form and return a copy to the study team in a way that is practical and convenient (e.g., email/scan or fax). The Informed Consent Form copy will be signed by the appropriate study team personnel obtaining re-consent and filed in the designated investigator site file location. In addition to a wet ink signature, this process will be documented in the Electronic Medical Record (EMR).

Demographic information (birth date, race, gender, etc), including smoking status.

- Medical/oncology history, including date of cancer diagnosis, prior treatments and any surgical procedures
- Physical examination of body system, height and weight
- ECOG performance status (Appendix A)
- Vital signs (blood pressure, pulse, and temperature)
- Prior and concomitant medications and any surgical procedure
- 12-lead ECG
- Hematology (hemoglobin, hematocrit, WBC and differential [with ANC], and platelet count) ≤7 days prior to first dose of rucaparib.
- Serum chemistry (total protein, albumin, creatinine or estimated GFR using Cockcroft Gault formula, BUN, total bilirubin, ALP, ALT, AST, glucose, sodium, potassium, chloride, CO₂, calcium and phosphorous) ≤7 days prior to the first dose of rucaparib.
- Serum pregnancy test for women of childbearing potential (≤3 days prior to the first dose of rucaparib)
- Urinalysis performed on freshly voided clean sample (dipstick for protein, glucose, blood, pH and ketones). If dipstick findings are abnormal based on investigator judgment, then a microscopic evaluation will be performed to assess the abnormal findings.

CONFIDENTIAL

This material is the property of the University of Pennsylvania.

- Tumor assessments should consist of clinical examination, appropriate imaging techniques including CT scans of the chest, abdomen and pelvis, with appropriate slice thickness per RECIST; other studies (MRI, X-ray, PET, and ultrasound) may be performed if required. The same method used to detect lesions at baseline is to be used to follow the same lesions throughout the clinical study. If a patient has known brain metastases, this disease should be evaluated at each required assessment.
- Patients will have coagulation tests PT/PTT/INR in advance of the clinical trial biopsy
- Tumor tissue biopsy if considered safe and feasible. Tumor tissue will be processed locally as formalin-fixed paraffin-embedded (FFPE) tissue. We are requesting 10-20 slides of tissue, 5-10um (preference for 20 slides, 10 um thick). Refer to the Laboratory Manual for detailed sample handling instructions.
- AE monitoring (after signing informed consent)

6.3 Treatment Phase

The following procedures should be completed before the first dose of oral rucaparib is administered, unless otherwise indicated.

6.3.1 Day 1 of Cycles 1 and 2

- Physical examination
- Weight
- ECOG performance status (Appendix A)
- Vital signs
- Concomitant medications and procedures
- Hematology
- Serum chemistry
- CA 19-9 measurement
- Serum or urine pregnancy \leq 3 days prior to start of cycle (for women of childbearing potential only). *(Note: a serum pregnancy test must be performed prior to the start of Cycle 1; a urine or serum pregnancy test is permitted prior to the start of Cycle 2)*
- AE monitoring
- Research blood sample
- Submission of an FFPE archival tumor tissue sample, if available. Refer to the Laboratory Manual for detailed sample handling instructions. *(Note: this sample is not required to be submitted on Cycle 1, Day 1, but should be submitted as soon as possible after a patient begins treatment with rucaparib)*
- Study drug accountability (Cycle 2 only)

Rucaparib tablets will be dispensed to the patient in sufficient quantity to last until Day 1 of the next treatment cycle. Patients will ingest rucaparib twice daily at about the same times every day as close to 12 hours apart as possible. Rucaparib should be taken with at least 8 oz (240 mL) of room temperature water with or without food. Patients will keep all unused tablets and containers (empty, partially used, and/or unopened) for accountability at the next visit. In the event of toxicities, re-treatment or dose modification will be according to the criteria described the protocol). Patients will record dosing information in their dosing diary.

6.1.2 Day 15 of Cycles 1 and 2

Patients will be instructed to refrain from taking their first dose of oral rucaparib at home on the day of their clinic visits because certain assessments must be performed prior to dosing.

- Hematology
- Serum chemistry
- Concomitant medications and procedures
- AE monitoring
- Study drug continuation

CONFIDENTIAL

6.1.3 Day 1 of Cycles 3 and Beyond

Patients will be instructed to refrain from taking their first dose of oral rucaparib at home on the day of their clinic visits because certain assessments must be performed prior to dosing.

The following procedures will be completed prior to oral rucaparib on Day 1 of Cycles 3 and beyond:

- Physical examination
- Weight
- ECOG performance status (Appendix A)
- Vital signs
- Concomitant medications and procedures
- Hematology
- Serum chemistry
- CA 19-9 measurement
- Research blood sample
- Serum or urine pregnancy (per investigator's discretion) <3 days prior to start of cycle (for WOCBP only)
- Disease/ tumor assessment (using the same methodology as was used at screening [eg, CT scan]) prior to the start of every odd numbered cycle (e.g. Cycle 3, 5, 7 etc.) (within 7 days before is permitted) relative to start of treatment on Day 1 of Cycle 1 through to 18 months on study, then every 16 calendar weeks (within 5 days before is permitted) relative to the start of treatment on Day 1 of Cycle 1. Timing of disease/tumor assessments is relative to Day 1 of Cycle 1 after enrollment.
- AE monitoring
- Study drug accountability.

Rucaparib tablets will be dispensed to the patient in sufficient quantity to last until Day 1 of the next treatment cycle. For patients being seen every other cycle, sufficient rucaparib for two cycles will be dispensed. Patients will ingest rucaparib twice daily at about the same times every day as close to 12 hours apart as possible. Rucaparib should be taken with at least 8 oz (240 mL) of room temperature water with or without food. Patients will keep all unused tablets and containers (empty, partially used, and/or unopened) for accountability at the next visit. In the event of toxicities, re-treatment or dose modification will be according to the criteria described the protocol). Patients will record dosing information in their dosing diary.

6.4 Day 1 of Cycles 11 and Beyond

Patients who reach C11D1 and are clinically stable as per the investigator, may elect to have blood work and office visits at odd cycles only (ie every other cycle). Imaging schedule will not change. Subjects will be required to have monthly hematology labs and can be performed locally and will be reviewed and assessed by a study Investigator. At each odd visit, patients will continue to have the evaluation as described in section 6.2.

6.5 Day 1 of Cycles 23 and Beyond

Patients who reach C23D1 and are clinically stable as per the investigator, may elect to have office visits, including imaging and clinical assessments, every 12 weeks instead of every 8 weeks. Subjects will still be required to have monthly hematology labs and can be performed locally and will be reviewed and assessed by a study investigator. Every 12 weeks, patients will continue to have the evaluation as described in section 6.4.

6.6 End of Treatment Visit

The following procedures will be performed for all patients as soon as possible after the last dose of oral rucaparib:

CONFIDENTIAL

- Physical examination
- Weight
- ECOG performance status (Appendix A)
- Vital signs
- Concomitant medications and procedures
- Hematology
- Serum chemistry
- CA 19-9 measurement
- Research blood sample
- Tumor scans if treatment was discontinued for reason other than radiologic disease progression
- Patients will have coagulation tests PT/PTT/INR in advance of the clinical trial biopsy
- A progression biopsy (if feasible and safe) For some patients this will not be end of treatment since they may be permitted to continue treatment beyond progression.
- AE monitoring
- Study drug accountability.

6.7 28-day Follow-up Visit

The following procedures will be performed for all patients at 28 (± 3) days after the last dose of oral rucaparib:

- AE monitoring (ongoing SAEs should be followed until resolution or stabilization)
- Tumor scans if not completed at end of treatment visit

6.8 Long-term Follow-Up

The following procedures will be performed for all patients every 8 weeks until death, loss to follow-up, withdrawal of consent from study or closure of study.

- Overall survival information. Follow-up can be performed via telephone.

6.9 Subject Withdrawal

Subjects may withdraw from the study at any time without impact to their care. They may also be discontinued from the study at the discretion of the Investigator for lack of adherence to intervention or study procedures or visit schedules, AEs, or due to (list protocol specific reasons that could arise here). The Investigator may also withdraw subjects who violate the study plan, or to protect the subject for reasons of safety or for administrative reasons. It will be documented whether or not each subject completes the clinical study. Subjects who withdraw early will have one final visit to collect investigational product and to follow up regarding adverse events.

6.9.1 Data Collection and Follow-up for Withdrawn Subjects

Subjects who withdraw consent to participate in the study will be seen for one final visit to collect the investigational product. During this visit they will be asked for permission to have the study team look into their survival status via publically available means.

7 Study Evaluations and Measurements

7.1 Medical Record Review

The following information will be extracted from the medical record of each subject prior to the first dose of rucaparib.

- Past medical/oncologic history including date of diagnosis, prior treatments, date of progression, and radiology and/or medical report(s) to support assessment of disease progression, and, if applicable, intolerable toxicity to chemotherapy.
- Detailed BRCA1/2 or PALB2 test results
- Detailed family history of all cancers

CONFIDENTIAL

This material is the property of the University of Pennsylvania.

7.2 Physical Examination

Physical examination will include all of the major body systems. Physical examinations will be performed at screening (complete) and at most study visits (limited as appropriate).

7.3 Body Weight and Height

Height will be measured during the Screening visit only. Weight will be measured per institutional guidelines.

7.4 Vital Signs

Vital signs will include blood pressure, pulse and body temperature. Vital signs will be performed at most study visits.

7.5 ECOG Performance Status

ECOG performance status (Appendix A) will be assessed at Screening, on Day 1 of each cycle, and at the End of Treatment visit. ECOG performance status should be assessed by the same study personnel at each visit, if possible. Care will be taken to accurately score performance status, especially during screening for study eligibility purposes. Additional consideration should be given to borderline ECOG performance status to avoid enrolling patients with significant impairment.

7.6 12-Lead Electrocardiogram

For all patients, 12-lead ECGs will be performed at Screening and at the End of Treatment. During the Treatment Phase, ECGs will be performed as clinically indicated.

All 12-lead ECGs will be analyzed locally.

7.7 Clinical Laboratory Evaluations

Certified local laboratories will perform study-related clinical laboratory tests according to institutional procedures, and the results will be reviewed by the investigator. The panels of laboratory tests to be performed are shown below:

Hematology: Hemoglobin, hematocrit, WBC and differential (with ANC), and platelet count at Screening, during treatment, and at the End of Treatment visit. Screening hematology results must be reviewed by the investigator prior to the start of treatment with rucaparib. During the treatment phase, results must be evaluated by the investigator and acted upon, as appropriate, within 24 hrs of receipt.

Clinical Chemistry: Total protein, albumin, creatinine or estimated GFR using the Cockcroft Gault formula, BUN or urea, total bilirubin, alkaline phosphatase (ALP), ALT, AST, glucose, sodium, potassium, chloride, CO₂, calcium, and phosphorus at Screening, during treatment, and at the End of Treatment visit. Screening clinical chemistry results must be reviewed by the Investigator prior to the start of treatment with rucaparib. During the treatment phase, results must be evaluated by the investigator and acted upon, as appropriate, within 24 hrs of receipt.

Urinalysis: Performed on freshly voided clean sample by dipstick for protein, glucose, blood, pH, and ketones per the schedule of evaluations. If dipstick findings are abnormal, then a microscopic evaluation will be performed to assess the abnormal findings. Urinalysis will be performed at screening only.

Serum/Urine Pregnancy: For women of childbearing potential only. Serum pregnancy test is to be performed ≤3 days prior to first dose of rucaparib and at the End of Treatment visit. Serum or urine pregnancy test (per investigator's discretion) is to be performed ≤3 days prior to the start of every cycle during the treatment phase.

Laboratory reports will be reviewed by the investigator or delegated physician who will then comment on out-of-range parameters and assess clinical significance. Clinically significant abnormalities and associated panel results, as well as results of any additional tests performed as follow-up to the

CONFIDENTIAL

abnormalities, will be documented on the eCRF as an AE. Refer to Section 9.4 for guidelines on reporting of abnormal laboratory values as AEs.)

7.8 Efficacy Evaluations

7.8.1 Tumor Assessments

Tumor assessments will be performed at Screening and within 7 days prior to the start of every odd numbered cycle (i.e., prior to the start of Cycles 3, 5, 7, etc.), until C11 and then every 12 weeks, and at the End of Treatment visit. If a CT scan was not performed at the End of Treatment visit, a CT scan should be performed at the 28-day Follow-up visit. Tumor response will be interpreted using RECIST Version 1.1 (Appendix B).

Tumor assessments should consist of clinical examination and appropriate imaging techniques (CT scans of the chest, abdomen, and pelvis with appropriate slice thickness per RECIST); other studies (MRI, X-ray, PET, and ultrasound) may be performed if required. If a patient has known brain metastases, this disease should be evaluated at each required assessment. The same methods used to detect lesions at baseline are to be used to follow the same lesions throughout the clinical study. Investigators should perform scans of the anatomical sites that, in their judgment, are appropriate to assess based on each patient's tumor status.

7.8.2 Tumor Markers

CA 19-9 will be collected on Day 1 of every clinical assessment date and at the End of Treatment visit.

7.9 Genetic Testing

All enrolled patients must have documented confirmation of a deleterious or suspected deleterious (or equivalent) mutation in BRCA1, BRCA2 or PALB2 as assessed by a CLIA certified local laboratory. Mutations may be somatic or germline. Mutations may have been assessed by germline testing, tumor biopsy or sequencing of circulating material (e.g Guardant360 testing).

7.10 Correlative Science

7.10.1 Research Blood Samples

Blood draws (up to 50mL of blood; 4 tubes, likely to include Streck tube and EDTA tube) for research will be collected on Day 1 of each Cycle and at the End of Treatment. Samples will very likely be analyzed for circulating tumor DNA and circulating tumor cells. An additional sample will be banked. Details will depend on available funds, samples and technology.

7.10.2 Tumor Tissue Analysis

Paired Tumor Biopsies: Tumor tissue biopsies will be obtained during screening and at time of disease progression, as deemed safe and feasible. It will be stored at an internal facility (refer to Lab Manual) to be used for analysis at a later date. Analysis may include:

- DNA extraction and sequencing in order to identify mutations in HR pathway genes, and evaluate whether a patient has a reversion mutation or other mutation(s) that may be associated with response or resistance to rucaparib.
- Analysis of genomic structural variation to determine a signature that may correlate with response or resistance to rucaparib.
- Additional or alternate assays depending on tissue availability and available technology.

Organoids: If feasible, organoids of tumor tissue will be created at the University of Pennsylvania and analyzed for genetic concordance with the parent samples. Other analyses may be conducted depending on practical constraints.

CONFIDENTIAL

This material is the property of the University of Pennsylvania.

Archival Tumor Tissue: If available, archival tumor tissue should be located during the screening process and submitted as soon as possible after a patient begins rucaparib.

Additional Tissue: If additional tissue or blood is available, it may be sent to Clovis Oncology for genetic analysis using the Foundation One platform or an alternative platform.

8 Statistical Plan

This is a single arm single stage Phase II study to evaluate progression-free survival rate at 6 months (PFS6) in 42 eligible patients. Patients who are not evaluable for efficacy, as defined within the protocol, will be replaced. Enrollment is expected to continue for 42 months and follow-up will continue for 6 additional months, prior to the final analysis of PFS. The null hypothesis is that the PFS6 rate is 44% (same as reported for standard therapies) and the alternative hypothesis is that the PFS6 rate has been increased to 60%.

8.1 Primary Endpoint

The primary study endpoint will be progression-free survival (PFS), defined as the time from start of study therapy to the occurrence of disease progression according to RECIST v1.1, as assessed by the investigator, or death from any cause. Patients who are alive and progression-free will be censored on the most recent date that documents progression-free status (ie., scan date or clinic visit date). The PFS6 will be estimated from the Kaplan-Meier curve.

8.2 Secondary Endpoints

The secondary endpoints are:

- (1) Objective response will be scored per RECIST v.1.1 as assessed by radiology review.
- (2) Objective response rate (ORR) is defined as the proportion of patients who achieve a complete or partial response, as determined by RECIST v1.1.
- (3) Duration of response (DOR) is defined as the time from first documentation of complete or partial response by RECIST v.1.1 to date of disease progression or death due to any cause. Responders who have not progressed will be censored on the most recent date that documents progression-free status.
- (4) Overall survival (OS) is defined as the time from start of study therapy to death due to any cause. Patients who are alive will be censored on the most recent date of patient contact.
- (5) The incidence of adverse events (AEs), clinical laboratory abnormalities and dose modifications.

8.3 Exploratory Endpoints

The exploratory endpoints include:

- (1) Gene sequence and structural rearrangements of tumor and circulating tumor DNA
- (2) Circulating tumor material concentrations summarized over time
- (3) Additional exploratory endpoints may be evaluated depending on sample availability and available technology.

8.4 Statistical Methods

Clinical Statistics: We plan to enroll 42 patients in a single-arm one-stage phase II design. Progression-free survival at 6 months (PFS6) will be the primary clinical outcome and it will be estimated using the Kaplan-Meier method. Based on prior research[1, 2, 21, 39] the null hypothesis is that the PFS6 rate in this population of subjects is 44%. The alternative hypothesis is that the PFS6 rate is 60%. Forty-two patients provide 81% power to detect this increase in PFS6, at a two-sided 5% significance level, assuming an exponential distribution and that enrollment will continue for 42 months with an additional 6 months of follow-up prior to the final statistical analysis. The confidence interval method will be used for the test of the primary hypothesis. A 2-sided 95% confidence interval for PFS6 will be constructed to determine whether the lower bound of this confidence interval excludes 44%, which is the historical control PFS6 rate. Secondary outcomes include overall survival (OS) and objective response rate (ORR); median OS and ORR will be estimated with 95% confidence intervals. Toxicities will be graded and tabulated and Grade 2 and Grade

CONFIDENTIAL

3 toxicity rates will be calculated. With 42 patients, we have 88% power to detect any toxicity occurring at a rate of 5% or more.

Translational Statistics: Genomic endpoints will also be assessed. Serial testing of the presence of mutations using tissue and peripheral blood will be described using graphical plots and descriptive statistics.

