We will enroll 42 patients in a single-arm phase II design. Progression-free survival rate at 6 months (PFS6) from the start of therapy will be the primary clinical outcome. A one sample test of the null hypothesis of a PFS6 rate equal to 44% versus the alternative hypothesis of a PFS6 rate equal to 60% will be conducted. With 42 patients enrolled over 42 months and with 6 months of additional follow-up, there is 81% power for the test assuming exponential survival and 5% 2-sided type I error rate.

Background and Study Rationale

This document is a protocol for a human research study. This study is to be conducted according to US and international standards of Good Clinical Practice (FDA Title 21 part 312 and International Conference on Harmonization guidelines), applicable government regulations and Institutional research policies and procedures.

Introduction

Pancreatic ductal adenocarcinoma (PDAC) is a highly lethal malignancy with a dismal prognosis. In metastatic disease, even our most commonly used first-line regimens (FOLFIRINOX and gemcitabine/abraxane) are associated with a median overall survival of <1 year[1, 2] and literature suggests that the progression free survival rate at 6 months (PFS6) is only 44% on standard therapy[2]. Secondly, for the patients who do remain responsive or stable on cytotoxic therapy, there does not currently exist a more manageable maintenance option. There is a great need to identify biomarkers that will predict response to specific treatments and to develop maintenance strategies for appropriately selected patients. BRCA1, BRCA2 and PALB2 mutations, whether somatic or germline, are found in patients with pancreatic cancer and may result in sensitivity to PARP inhibitors, particularly in the absence of platinum-resistance.

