3.1.4 Follow Up Phase

All patients will have a 28-day follow-up period for AEs following the last dose of rucaparib. CT scans at 28-day follow-up should also be performed for patients who discontinued treatment for reason other than disease progression and did not have a radiologic assessment at the End of Treatment visit. After the 28-day follow-up visit, patients will be followed for survival every 8 weeks until death, loss to follow-up, withdrawal of consent, or study closure.

CONFIDENTIAL

This material is the property of the University of Pennsylvania.

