3.1.5 Study Schema

3.1.6 End of Study

The trial will be completed when all enrolled patients have completed 6 cycles of treatment or have experienced progressive disease (PD), whichever occurs first.

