3.2 Study Endpoints

3.2.1 Primary Study Endpoints

The primary study endpoint will be the PFS rate at 6 months (PFS6) as determined from a Kaplan-Meier curve. PFS defined as the time from start of study therapy to the occurrence of disease progression according to RECIST v1.1, as assessed by the investigator, or death from any cause. Patients who are alive and progression-free will be censored on the most recent date that documents progression-free status (i.e. scan date or clinic visit date).

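### The stated 81% power belongs to a constant-hazard test on all PFS events; the planned Kaplan-Meier confidence-interval test has about 47% or 59% power at a true PFS6 of 60%

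*Combined protocol and SAP*

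**What the plan says.** Section 8.4 (Statistical Methods) sets a null PFS6 of 44% against an alternative of 60% and gives the power: "Forty-two patients provide 81% power to detect this increase in PFS6, at a two-sided 5% significance level, assuming an exponential distribution". It adds 42 months of enrolment and 6 further months of follow-up. The Statistical Methodology entry of the Study Summary makes the same claim: "there is 81% power for the test assuming exponential survival and 5% 2-sided type I error rate".

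The estimator is Kaplan-Meier throughout. Section 3.2.1: "The primary study endpoint will be the PFS rate at 6 months (PFS6) as determined from a Kaplan-Meier curve". Section 8.1: "The PFS6 will be estimated from the Kaplan-Meier curve". Section 8.4 names Kaplan-Meier as well and gives the decision rule: "A 2-sided 95% confidence interval for PFS6 will be constructed to determine whether the lower bound of this confidence interval excludes 44" percent. It does not say how the interval is built (plain, log, log-log or other). No section plans an exponential-model estimate or a one-sample hazard test, and no formula or software is cited for the 81%.

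**The concern.** The power statement and the test appear to describe two different analyses. A power calculation that assumes exponential survival, and that needs the accrual period as an input, draws on every PFS event up to month 48. A Kaplan-Meier estimate at month 6 gains nothing from events after month 6. Since every patient has at least 6 months of potential follow-up, the 42-month accrual period adds nothing to its precision.

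This is the trial's only confirmatory test. If the stated power is too high, a negative result will be read as stronger evidence against a 60% rate than it is. The unnamed interval is a second problem. In an open-label single-arm trial, a success threshold that depends on an unstated choice could be settled after the data are seen.

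**Working it through.** **Inputs.** From section 8.4 and the Study Summary: n = 42, PFS6 of 44% against 60%, two-sided 5%, exponential survival, 42 months of accrual plus 6 of follow-up. From 3.2.1, 8.1 and 8.4: Kaplan-Meier PFS6, success if the lower 95% limit exceeds 44%. Assumed here: uniform accrual, and, where stated, a dropout rate, because the documents give none.

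**1. Reproducing 81%.** Monthly hazards are λ = −ln(S)/6:
- null: −ln(0.44)/6 = 0.1368
- alternative: −ln(0.60)/6 = 0.0851
- hazard ratio 0.622, log ratio 0.4745 in absolute value

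Expected events are D = 42 × [1 − (e^(−6λ) − e^(−48λ))/(42λ)]. Under the alternative this is 42 × [1 − (0.6000 − 0.0168)/3.576] = 35.15. Under the null it is 38.79.

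Power of a log-hazard test on all events:
- alternative variance: Φ(0.4745 × √35.15 − 1.96) = Φ(0.853) = 80.3%
- null variance for the critical value: Φ(√35.15 × (0.4745 − 1.96/√38.79)) = 82.8%
- simulated exponential-model interval: about 80%

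The stated 81% sits inside this range.

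**2. Information available to the planned test.** Events expected by month 6 under the alternative are 42 × 0.40 = 16.8, just under half of the 35.15.

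**3. Success threshold of the planned test.** If nobody is censored before month 6, the Kaplan-Meier estimate is x/42 and the Greenwood variance is the binomial variance. With p = x/42, the lower limits are:
- plain: p − 1.96√(p(1−p)/42)
- log: p × exp(−1.96 s), with s = √((1−p)/(42p))
- log-log: p^exp(1.96 s/|ln p|)
- Wilson and exact (Clopper-Pearson): standard formulas

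| Progression-free at month 6 | Plain | Log | Wilson | Log-log | Exact |
|---|---|---|---|---|---|
| 24/42 (57.1%) | 42.2% | 43.98% | 42.2% | 40.9% | 41.0% |
| 25/42 (59.5%) | 44.7% | 46.4% | 44.5% | 43.2% | 43.3% |

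At 26/42 (61.9%) all five exceed 44%. Plain, log and Wilson therefore need 25/42, and log-log and exact need 26/42. At exactly 25/42 the interval type alone decides the trial.

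**4. Power and size of the planned test** (exact binomial, n = 42):

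| Rule | Power at 60% | One-sided size at 44% | True PFS6 for 81% power |
|---|---|---|---|
| at least 25/42 | 59.1% | 3.1% | about 65% |
| at least 26/42 | 46.7% | 1.5% | about 67% |

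The shortfalls are 81 − 59.1 = 21.9 and 81 − 46.7 = 34.3 points. A cutoff of 23/42 would give 80.3% power, but its one-sided size is 10.6%, so it cannot be a two-sided 5% test.

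**5. Early censoring.** Section 3.2.1 censors at the last date that documents progression-free status, and section 3.1.4 reads: "After the 28-day follow-up visit, patients will be followed for survival every 8 weeks until death". Section 3.1.6 reads: "The trial will be completed when all enrolled patients have completed 6 cycles of treatment", or have progressed if sooner; six 28-day cycles are 168 days, short of six months. Some censoring before month 6 is therefore possible. Simulated power at a true 60% (60,000 trials, assumed exponential dropout by month 6):

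| Dropout by month 6 | Plain | Log | Log-log | All-events exponential interval |
|---|---|---|---|---|
| 0% | 59.1% | 59.1% | 46.3% | 80.2% |
| 5% | 55.3% | 62.5% | 47.6% | 77.6% |
| 10% | 54.0% | 62.8% | 46.1% | 74.9% |
| 15% | 52.7% | 61.9% | 44.6% | 72.2% |

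No Kaplan-Meier interval exceeds about 63%. The log interval's small gain comes with a larger one-sided size, about 4.7% at 10% dropout in a separate simulation of 20,000 trials.

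**6. Sample size for 81% at a true 60%,** with no early censoring. Power moves in steps with n. It first reaches 81% at n = 65 (log), 72 (plain or Wilson) or 79 (log-log or exact). It stays there from 71, 78 and 85 respectively.

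**The case against.** **Scan timing.** Scans fall in the 7 days before each odd-numbered cycle (sections 6.1, 6.1.3 and 7.8.1). The last one before month 6 is therefore at about day 161 to 168, and the next at about day 217 to 224. If progression were recorded only at scans, a true exponential 60% at day 182.6 would appear as 0.60^(168/182.6) = 62.5% up to 0.60^(161/182.6) = 63.7%. Power would then be about 71% to 77% (25/42 rule) or 60% to 66% (26/42 rule). A true 44% would appear as about 47% to 48.5%, with one-sided size of about 7% to 10% or 3.7% to 5.6%.

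This does not rescue the 81%, since even the best case is lower. The hypotheses are also stated for PFS6 as the protocol measures it, that is, RECIST progression read from the Kaplan-Meier curve. On that reading 59.1% and 46.7% apply. What stands is that these powers, and the sizes of 3.1% and 1.5%, refer to the recorded rate and should be stated that way.

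**An exponential interval may be intended.** The interval sentence in 8.4 does not itself say Kaplan-Meier, and an exponential-model interval would give about 80%. But Kaplan-Meier is the only estimator named, in three sections, and nothing in the documents supports a parametric interval. If one were intended, the text would still need correcting.

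**The repair is a choice.** The primary test could instead be changed to match the power. That is possible, but it would make the primary conclusion depend on a constant hazard. Restating the power is the smaller change.

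**Conclusion.** The concern holds. The 81% is correct arithmetic for a constant-hazard test on about 35 events, but the plan does not contain that test. For the test it does contain, power at a true PFS6 of 60% is 59.1% or 46.7% depending on the unnamed interval, and about 45% to 63% under an assumed 5% to 15% dropout by month 6. The observed PFS6 must itself be about 60% or more for success, so at the design alternative the trial is close to a coin toss.

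The exact figures assume n = 42, no censoring before month 6, and 44% and 60% understood as recorded rates. That the 81% came from an all-events calculation is inferred from the inputs; the shortfall does not depend on that inference.

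The consequence falls on a negative result. Under the same assumptions a positive result is not undermined, with one-sided size 3.1% or 1.5%, although 3.1% is slightly above the nominal 2.5%.

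**What to change.** Keep the Kaplan-Meier confidence-interval test and make two changes.

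1. In section 8.4, name the interval type for PFS6 before the data are analysed.
2. In section 8.4 and the Study Summary, replace 81% with the power of the named interval: about 59% at a true 60% for plain, log or Wilson (81% at a true rate of about 65%), or about 47% for log-log or exact (81% at about 67%). State that the figure refers to PFS6 as recorded and assumes no censoring before month 6, and give the range under a stated dropout assumption.

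The cost is wording in two places, with no extra patients and no change of primary test. The stated power becomes less favourable, and the scientific review committee may ask about the sample size as a result; step 6 of the working gives the numbers for that discussion.
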